6.4.7. Subgroup Analysis

Analysis of efficacy and safety will also be performed for subgroups of interest including:

Table 3: Subgroups for Analysis

Table # [1]		Categories and comm	nents		
1	Gender	Male	Female		
2	Age #1	$< 65 \text{ vs} \ge 65 \text{ years}$			
3	Age #2	$< 75 \text{ vs} \ge 75 \text{ years}$			
4	Body mass index #1	≤ vs > median			
5	Body mass index #2	Quartiles			
6	Race	White	Black	Other	
7	Baseline statin use	Yes	No		
8	Baseline statin intensity	High intensity	Not high intensity		
9	Other lipid management therapy	Any statin with other lipid management therapy	No statin but other lipid management therapy	No lipid management therapy	
10	Baseline triglyceride level #1	<200 mg/dL vs ≥200 mg/dL			
11	Baseline triglyceride level #2	≤ vs > median			
12	Metabolic disease [2]	Diabetes	Metabolic syndrome without diabetes	Neither	
13	ASCVD status [3]	ASCVD	ASCVD risk equivalents		
14	Renal impairment by eGFR categories - mL/min/1.73m ² [4]	≥15 to <30	≥30 to <60	≥60 to <90	≥90
15	History of allergy [5]	Yes	No		
16	Baseline LDL-C #1	≤ vs > median			
17	Baseline LDL-C #2	Quartiles			
18	Study center region	North America	Europe	South Africa	
19	Post baseline LDL-C [6]	<pre><25 at any time point vs >25 mg/dL at all time points</pre>			
20	Phenotype [7]	FH	Non-FH		
21	Baseline ezetimibe use	Yes	No		

- [1] Numbers provide the order that the subgroups will be presented.
- [2] Metabolic syndrome is not based on medical history but will be defined according to the American Heart Association (AHA) definition (see Reference 1).
- [3] Derived from the targeted medical history page: CHD=Yes or CVD=Yes or PAD=Yes then the subject is ASCVD; all other subjects are ASCVD risk equivalent
- [4] Creatinine clearance (CrCl) values using the Cockroft and Gault estimation:
- $CrCl = \{((140-age) \times weight)/(72xSerum Creatinine)\} \times 0.85 \text{ (if female)}$
- [5] A history of allergy was identified using the following high-level group term (HLGT): allergic conditions.
- [6] For descriptive summary of PCSK9 data only.
- [7] Phenotype is defined using Simon Broome diagnostic criteria (see Appendix A in protocol). Definite Familial Hypercholesterolemia (FH) and Possible Familial Hypercholesterolemia will be included as FH.

Baseline variables to be analyzed by subgroup:

Disposition	
Protocol Deviations	

Demographics and Baseline Characteristics
Targeted Medical History
Other Medical History
Medical History of Partial or Complete Statin Intolerance
Study Drug Administration
Day 1 Concomitant Medications
New or Changed Concomitant Medications
Prior Medications
Prior Lipid Modifying Therapies
Day 1 Lipid Modifying Therapy Usage
New or Changed Lipid Modifying Therapy Usage
Shift from Baseline in Statin Intensity

Safety variables to be analyzed by subgroup:

Treatment Emergent Adverse Events
Treatment Emergent Serious Adverse Events
Treatment Emergent Adverse Events at the Injection Site
Withdrawals due to TEAEs

Efficacy variables to be analyzed by subgroup:
Co-Primary #1: Percentage change in LDL-C from baseline to Day 510 – ANCOVA – Washout
Imputation
Co-Primary #2: Time adjusted percentage change in LDL-C from baseline after Day 90 and up to Day
540. This is the average percentage change in LDL-C from baseline over the period after Day 90 and up
to Day 540 – MMRM – control-based PMM
Key Secondary #1: Absolute change in LDL-C from baseline to Day 510 – MMRM – control-based
PMM
Key Secondary #2: Time adjusted absolute change in LDL-C from baseline after Day 90 and up to Day
540 – MMRM – control-based PMM
Key Secondary #3: Percentage change from baseline to Day 510 in PCSK9, total cholesterol, ApoB, and
non-HDL-C – MMRM – control-based PMM
Other Secondary #3: Actual value, absolute change and percentage change in LDL-C from baseline to
each assessment time up to Day 540 – Descriptive Stats

Other Secondary #6: Actual value, absolute change and percentage change in other lipids, lipoproteins, apolipoproteins, and PCSK9 from baseline at each subsequent visit to Day 540 – MMRM

Other Secondary #6: Actual value, absolute change and percentage change in other lipids, lipoproteins, apolipoproteins, and PCSK9 from baseline at each subsequent visit to Day 540 – Descriptive Stats*

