4.2. Inclusion Criteria

Subjects may be included in the study if they meet all of the following criteria:

1. Male or female subjects ≥ 18 years of age.
2. History of HeFH with a diagnosis of HeFH by genetic testing; and/or a documented history of untreated LDL-C of >190 mg/dL, and a family history of FH, elevated cholesterol or early heart disease may indicate FH ([APPENDIX A](#))
3. Stable on a low-fat diet (eg, NCEP)
4. Serum LDL-C ≥ 2.6 mmol/L (≥ 100 mg/dL) at screening
5. Fasting triglyceride <4.52 mmol/L (<400 mg/dL) at screening.
6. Calculated glomerular filtration rate >30 mL/min by estimated glomerular filtration rate (eGFR) using standardized clinical methodology.
7. Subjects on statins should be receiving a maximally tolerated dose. Maximum tolerated dose is defined as the maximum dose of statin that can be taken on a regular basis without intolerable adverse events. Intolerance to any dose of any statin must be documented as historical AEs attributed to the statin in question in the source documentation and on the Medical History page of the electronic case report form (eCRF) (see [APPENDIX B](#)).
8. Subjects not receiving statin must have documented evidence of intolerance to all doses of at least two different statins (see [APPENDIX B](#)).
9. Subjects on lipid-lower therapies (such as a statin and/or ezetimibe) should be on a stable dose for ≥ 30 days before screening with no planned medication or dose change during study participation.
10. Subjects must be willing and able to give informed consent before initiation of any study-related procedures and willing to comply with all required study procedures.

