6.4.8.2. Laboratory Tests

Laboratory values will be summarized by treatment group, including the observed value, changes and percent changes from baseline at each time point.

A shift analysis using the normal range (except for eGFR and HbA1c) will be done which counts the number of subjects with a low, normal or high value at baseline and a low, normal or high value post baseline.

The following ranges will be used for eGFR and HbA1c

- For eGFR, the categories will be Severe = $<30 \text{ mL/min}/1.73\text{m}^2$; Moderate = $\ge 30 \text{ to } <60 \text{ mL/min}/1.73\text{m}^2$; Mild = $\ge 60 \text{ to } <90 \text{ mL/min}/1.73\text{m}^2$; and Normal = $\ge 90 \text{ mL/min}/1.73\text{m}^2$.
- For HbA1c, the categories will be $\leq 5.6\%$, $\geq 5.7\%$ to $\leq 6.4\%$, and $\geq 6.5\%$.

The baseline and worst post-baseline value will be utilized for the shift tables. Note that the shift table dealing with the fasting glucose parameter will require the lab sample to be taken while fasting. Samples taken while the subject was not fasting will not be analyzed.

The number and percentage of subjects with potentially clinically significant (PCS) laboratory values and clinically significant (CS) laboratory values (refer to Appendix 4 for the criteria) will be summarized by treatment group. Hemoglobin A1c criteria is explicitly stated in Appendix 4. All other PCS and CS criteria are met when both of the following occur:

- Post-baseline values meet the thresholds listed in Appendix 4
- Baseline values or any prior post-baseline values do not meet the thresholds listed in Appendix 4

PCS chemistry laboratory values will also be classified as follows:

- Abnormal baseline:
 - Non HbA1c: >1 and \leq 3x ULN at baseline and >1 and \leq 3x ULN at final visit
 - o HbA1c: ≥6.5% at baseline and ≥6.5% and ≥0.5% change from baseline at final visit

• Elevated further:

○ Non HbA1c: >1 and \leq 3x ULN at baseline or post baseline and becoming > 3x ULN post baseline

• Final visit:

- Non HbA1c: >1 and \leq 3x ULN at final visit only but not at baseline or previous visits
- o HbA1c: \geq 6.5% and \geq 0.5% change from baseline at final visit only but not at baseline or previous visits

• Persistently elevated:

- Non HbA1c: >1 and \leq 3x ULN at a post baseline visit and remains >1 and \leq 3x ULN until final visit

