2.4. Statin/LMT Use at Baseline

The small number of subjects who were not currently using statins or other lipid-modifying therapies (LMT) at baseline caused convergence issues with the imputation models. As such, the statin/LMT use at baseline effect was removed from the multiple imputation washout model and Control Based - Pattern Mixture Model imputation steps. Note that the statin/LMT use at baseline effects were already removed from the analysis models.

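### Two Table 3 subgroup definitions need correcting: row 9 gives no separate class to a statin taken alone, and row 14 labels Cockcroft-Gault clearance as eGFR per 1.73 m²

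*SAP*

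**What the plan says.** **Row 9** of SAP Table 3 (section 6.4.7) concerns other lipid management therapy and has three categories: "Any statin with other lipid management therapy", "No statin but other lipid management therapy" and "No lipid management therapy". Row 7 splits by baseline statin use, row 8 by statin intensity and row 21 by ezetimibe use.

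Protocol 4.2 accepts subjects on a statin, on ezetimibe, or on both. Protocol Appendix B makes a highly effective statin the default background and does not require a second agent. SAP Addendum 2.4 attributes convergence problems in the imputation models to "The small number of subjects who were not currently using statins or other lipid-modifying therapies (LMT) at baseline".

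**Row 14** is headed "Renal impairment by eGFR categories", in mL/min/1.73 m². Its note [4] defines the values as "Creatinine clearance (CrCl) values using the Cockroft and Gault estimation" and prints the formula, which uses age, weight, serum creatinine and sex. SAP 6.4.8.2 sets shift-table classes for eGFR itself ("For eGFR, the categories will be Severe" and upwards) with cut-points at 30, 60 and 90 mL/min/1.73 m². Laboratory eGFR is a separate parameter in the chemistry panel (SAP 3.8.8.3) and a listed baseline characteristic (SAP 6.4.3).

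Addendum 2.2 changes the statin-intensity subgroup only and leaves rows 9 and 14 as they were.

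**The concern.** A subgroup table is only as useful as its class definitions. In row 9 a programmer must decide where a statin-only subject goes, and the wording permits more than one answer. Depending on that decision, these subjects drop out of the row, appear under a label saying they take no lipid therapy, or are merged with those on combination therapy. In row 14 a reader would take the classes to be indexed eGFR and could set them beside the 6.4.8.2 tables, when the row holds an unindexed clearance.

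At stake is the meaning of the classes. The co-primary and key secondary tests do not use them. Both arms are classified by the same rule, so a between-arm comparison within a class is not biased by the definition.

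**Working it through.** The plan gives no figure here to reproduce. The check is whether the categories cover the eligible subjects and whether label and formula agree.

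**Row 9, coverage.** Cross statin (yes/no) with other lipid therapy (yes/no) under three readings. Classes 1, 2 and 3 are the categories in the order listed.

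| Statin | Other therapy | Literal | Last cell means no *other* therapy | First cell means statin with or without other therapy |
|---|---|---|---|---|
| Yes | Yes | 1 | 1 | 1 |
| Yes | No | none | 3 | 1 |
| No | Yes | 2 | 2 | 2 |
| No | No | 3 | 3 | 3 |

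The literal reading covers three of four combinations. The second covers all four but puts statin users under a label of no therapy. The third covers all four and labels the last cell correctly, but class 1 then repeats row 7 *Yes* and its wording is wrong. No reading isolates a statin taken alone. Rows 7, 8 and 21 are one-way splits and do not isolate it either.

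**Row 9, possible size.** Inputs: 482 enrolled; statin-intolerant enrolment capped at 15% (Protocol 3.1); subjects off statins must be statin intolerant (Protocol 4.2). Assume the cap held at the final enrolment.

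- Maximum without a statin: 0.15 × 482 = 72.3, so 72. Minimum on a statin: 482 − 72 = 410.
- The statin-alone share is not given. Assume 20%, 50% and 80% of the 410: 82, 205 and 328 subjects.
- Literal reading: 82, 205 or 328 unclassified.
- Second reading, minimum share of the last cell taking a statin: 82/(82 + 72) = 53%, 205/(205 + 72) = 74%, 328/(328 + 72) = 82%. These are minima because all 72 are counted as untreated, whereas Addendum 2.4 calls that group small.
- Third reading: zero unclassified and zero mislabelled.

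**Row 14, unit.** Note [4] gives CrCl = (140 − age) × weight / (72 × serum creatinine), × 0.85 if female. Weight is in the numerator and there is no body-surface-area (BSA) term. With weight in kg (assumed) and creatinine in mg/dL (the unit in SAP Appendix 4), the result is in mL/min. Indexing would require multiplying by 1.73/BSA. For assumed BSA values, 60 mL/min becomes:

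- 1.5 m²: 60 × 1.73/1.5 = 69.2
- 2.0 m²: 60 × 1.73/2.0 = 51.9
- 2.3 m²: 60 × 1.73/2.3 = 45.1

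Two assumed subjects show a change of class:

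- Man, 55 years, 95 kg, creatinine 1.0: 85 × 95/72 = 112.2 mL/min (≥90). At BSA 2.2 m², 112.2 × 1.73/2.2 = 88.2 (60 to <90).
- Woman, 60 years, 50 kg, creatinine 0.8: 80 × 50/(72 × 0.8) × 0.85 = 59.0 mL/min (30 to <60). At BSA 1.5 m², 59.0 × 1.73/1.5 = 68.1 (60 to <90).

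This shows only that indexing can move a subject across a cut-point. It does not measure a discrepancy in this trial.

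**Reach.** SAP 6.4.7 lists 14 baseline, 4 safety and 8 efficacy entries to be analysed by subgroup: 14 + 4 + 8 = 26. Five of the efficacy entries (two co-primary, three key secondary) use imputed data.

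**The case against.** The sponsor could say that row 9's intent is clear enough: either the last cell means no other therapy, given the row's title, or the first cell means any statin. Either is plausible, and on the second nobody is lost or mislabelled. That limits the size of the point but does not remove it. The two intentions put the same subjects in different cells and the text does not choose. The typeset table should be checked for a fourth cell, but row 14 shows all four of its categories, so nothing suggests that one was lost.

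For row 14, the formula is printed under the table, so a careful reader can see what was computed. That is fair, but the row heading and unit still contradict the note.

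Four stronger conclusions might be inferred, and the documents do not support them:

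- **That a large block of subjects is certainly excluded.** The counts above depend on the reading and on assumed shares.
- **That 6.4.8.2 uses a different renal measure.** The documents give no eGFR equation, so only a mismatch of label and unit is shown.
- **That row 14 leaves a material gap below 15.** Entry required "Calculated glomerular filtration rate >30 mL/min by estimated glomerular filtration rate (eGFR"), which makes such a baseline value implausible. The 6.4.8.2 shift table needs an open lowest class because it also uses worst post-baseline values; a baseline subgroup does not.
- **That each row feeds 26 outputs.** The 26 are list entries, and Addendum 2.2 says that only select variables are summarised by subgroup.

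**Conclusion.** Both definitions are wrong as worded, and the consequence is minor. Row 9 either omits statin-only subjects, mislabels them, or merges them with combination users, and on no reading does it show their result. How many are affected cannot be determined from the documents: from zero up to the illustrative 82, 205 or 328 unclassified, assuming the cap held and statin-alone shares of 20%, 50% and 80%. Row 14 carries the wrong name and unit for the quantity that its note defines, so its classes need not agree with those in SAP 6.4.8.2; the extent of any disagreement here is unknown. The label mismatch needs no numerical assumption. The effect is confined to subgroup tables.

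**What to change.** **Row 9.** Add a category for *statin without other lipid management therapy* and keep the last category for subjects on no lipid therapy at all, so that the four classes cover every combination. The untreated class may be very small. State that it will be described only, without ANCOVA or MMRM, if it cannot support those models.

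**Row 14.** Relabel the row as CrCl (Cockcroft-Gault) in mL/min. Classifying by the collected baseline eGFR instead is optional, and only after its unit is confirmed, because Protocol 4.2 states eGFR in mL/min while the SAP uses mL/min/1.73 m².

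**Record.** The Addendum's introduction says that the database is locked and the study unblinded, so document both changes as post hoc. A count of subjects by old and new class for any reclassified row is enough; the outputs need not be shown twice.

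**Cost.** No new data are needed. Relabelling row 14 changes table text only. Reclassifying row 9, or row 14 if eGFR is chosen, means rerunning up to 26 list entries per row, fewer if only select variables were produced. Five of those entries use imputed datasets that already exist.

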6.4.8. Safety Analysis

The safety objectives of this study are to evaluate the safety and tolerability profile of inclisiran.

6.4.8.1. Adverse Events

The Medical Dictionary for Regulatory Activities (MedDRA) dictionary (v20.1) will be used for coding AEs. An AE (classified as preferred term) occurring during the treatment period will be counted as a treatment emergent AE (TEAE) either if it is not present at Day 1 before treatment or if it is present before treatment but increased in severity during the treatment period.

The following summary tables will be presented:

• Overall Summary of TEAEs

^{*} Post baseline LDL-C subgroup included for PCSK9 summary table only.

- TEAEs by SOC and PT
- TEAEs by PT
- Common (2% within either treatment group) by PT
- TEAEs by SOC, PT, and Severity
- TEAEs by SOC, PT, and Relationship to Study Drug
- Related TEAEs by SOC, PT, and Severity
- Treatment Emergent Serious AEs (TESAEs) by SOC and PT
- TESAEs by PT
- TESAEs by SOC, PT, and Severity
- TESAEs by SOC, PT, and Relationship to Study Drug
- Related TESAEs by SOC, PT, and Severity
- TEAEs Leading to Withdrawal of Study Treatment by SOC and PT
- TEAEs with a Fatal Outcome by SOC and PT

If more than one event occurred with the same preferred term for the same subject, the subject will be counted only once for that preferred term using the most severe or related occurrence for the summary by severity, or relationship to study drug, respectively.

For common (2% within either treatment group) TEAEs, serious TEAEs and TEAEs leading to withdrawal of study medication, risk ratios along with 95% confidence intervals will be presented to compare treatment groups with respect to risk.

The following additional adverse events (Refer to Appendix 5, Additional Adverse Events Investigations) will also be assessed:

- 1. Adverse Events at the Injection Site
- 2. Hepatic events
- 3. Renal events
- 4. Hypersensitivity
- 5. Neurological events and Neurocognitive disorders
- 6. Ophthalmological events

Clinically relevant TEAEs at the injection site will also be tabulated. See Appendix 6 for a list of clinically relevant injection site preferred terms.

The time to the first TEAE at the injection site will also be summarized. Only subjects with a TEAE at the injection site will be included in the analysis. The time (hours) will be calculated from the date of the most recent administration of study drug. The duration of the TEAE will also be summarized. The same analyses will be performed for each individual TEAE PT at the injection site. The time to the first clinically relevant adverse event at the injection site will be analyzed similarly.

Any immune-related events will be identified in the SOC of immune system disorders.

Listings will be presented for subjects with SAEs/AEs leading to a discontinuation or death. Listings of SAEs and Death will also be provided.

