Reference Therapy, Dose, and Mode of Administration: Placebo will be administered as SC injections of saline solution. Placebo volume will be matched to test product volume within each dose and injection ie, the 300 mg dose will be administered as 1.5 mL of placebo.

Criteria for Evaluation:

Efficacy:

Primary Endpoints:

- Percentage change in LDL-C from baseline to Day 510
- Time adjusted percentage change in LDL-C from baseline after Day 90 and up to Day 540. This is the average percentage change in LDL-C from baseline over the period after Day 90 and up to Day 540.

Key Secondary Endpoints:

- Absolute change in LDL-C from baseline to Day 510
- Time adjusted absolute change in LDL-C from baseline after Day 90 and up to Day 540
- Percentage change from baseline to Day 510 in PCSK 9, total cholesterol, ApoB, and non-HDL-C

Other Secondary Endpoints:

- Mean maximum percentage change in LDL-C
- Absolute change from baseline to Day 510 in PCSK9, total cholesterol, ApoB and non-HDL-C
- Absolute change and percentage change in LDL-C from baseline to each assessment time up to Day 540
- Individual responsiveness defined as the number of subjects reaching on treatment LDL-C levels of <25 mg/dL, <50 mg/dL, <70 mg/dL, and <100 mg/dL at Day 510
- Proportion of subjects in each group with greater or equal to 50% LDL-C reduction from baseline
- Absolute change and percentage change in other lipids, lipoproteins, apolipoproteins, and PCSK9 from baseline at each subsequent visit to Day 540
- Proportion of subjects in each group who attain global lipid targets for their level of atherosclerotic cardiovascular disease (ASCVD) risk

Exploratory Endpoints:

- Incidence of CV death, resuscitated cardiac arrest, non-fatal MI, and non-fatal stroke (ischemic and hemorrhagic)
- Response of LDL-C reduction by underlying causal mutations of HeFH

Safety: Adverse event, SAEs, vital signs, clinical laboratory values (hematology, coagulation testing, chemistry, and urinalysis), and electrocardiograms (ECGs) will be collected at specified visits through the EOS visit (Day 540). Cardiovascular events will be reported as AEs for the compilation of information on CV events such as CV death, resuscitated cardiac arrest, non-fatal MI, and non-fatal stroke (ischemic and hemorrhagic). In addition, formation of ADA and subsequent characterization of ADA will be evaluated for the investigational product.

Statistical Methods:

Sample Size and Power

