1.2.2.2. Clinical

Inclisiran has been studied in one completed Phase I (ALN-PCSSC-001) study (N=69) and one Phase II (ORION-1) study (N=501); dosing has completed in ORION-1 and the extended follow-up is ongoing.

ALN-PCSSC-001: Doses up to 800 mg as a single dose and two doses or more doses up to 500 mg were administered.

ORION-1: Up to 500 mg as a single dose on Day 1 or two doses on Day 1 and Day 90 (100 mg, 200 mg or 300 mg) were administered.

The efficacy data generated in these two studies show robust and prolonged reductions in PCSK9 and LDL-C levels in plasma. PCSK9 was reduced from baseline by around 75%. Mean LDL-C was reduced by around 50% with one dose of 300 mg and 55% with two doses of 300 mg given 30 or 90 days apart in both the Phase I and the ORION-1 study, respectively. This effect is still significant 210 days after a single dose and remains at around a mean of 50% when measured 120 days after the second dose given at Day 90 in the ORION-1 study. Other lipids and lipoproteins are also modified as would be expected from a drug acting on PCSK9 with a potentially beneficial modification of the overall atherogenic lipid profile [Ray et al, 2017].

To date, no clinically relevant safety concerns have arisen in these studies of inclisiran; collection and analysis of data up to Day 360 is ongoing in the ORION-1 (Phase II) study.

Based on these efficacy and safety data, 300 mg has been selected as the dose for subsequent clinical studies with a dosing at Day 1, Day 90, and every 6 months subsequently.

Safety:

In the ongoing Phase II (ORION-1) study with a follow up of more than 210 days, single doses of up to 500 mg on Day 1 or two doses (100 mg, 200 mg or 300 mg) (given 90 days apart) were also generally well tolerated and the majority of adverse events (AEs) in inclisiran-treated subjects with ASCVD and ASCVD risk equivalents were mild or moderate in intensity. Injection site reactions have been reported in around 5% of subjects receiving either one or two doses of inclisiran [Ray et al, 2017]. The emerging safety profile will be further evaluated in the ongoing Phase II (ORION 1) study and the subsequent planned studies.

Efficacy:

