1.3. Known and Potential Risks and Benefits

Subjects taking part in this clinical study will receive guideline recommended standard of care as background therapy (including maximally-tolerated statin therapy and/or other LDL-C lowering therapies) when administered inclisiran or placebo. Reduction of LDL-C has been associated with reduced CV risk both by epidemiology and in controlled clinical trials. Injection site reaction is the only event known to be attributed to inclisiran treatment. The safety profile of inclisiran observed to date is considered acceptable for this clinical trial.

An expanded risk-benefit summary is provided in the IB [[Investigator's Brochure](#)].

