6.2. Randomization

Subjects will be screened and approximately 400 eligible subjects will be randomized by the IRT system: 200 subjects will be randomized to inclisiran sodium 300 mg and 200 subjects randomized to placebo. Due to faster than expected enrollment, actual enrollment was 482 subjects. Treatment allocation will be stratified by country and by current use of statins or other lipid-modifying therapies. Each subject will receive four subcutaneous (SC) injections of blinded inclisiran or placebo on Day 1, Day 90, Day 270, and Day 450.

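### The risk ratio is the only planned between-arm safety contrast; it has no finite value when all events fall on inclisiran, and the pooled injection-site group has no contrast at all

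*SAP*

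**What the plan says.** SAP 6.4.8.1 sets the between-arm comparison of adverse events in one sentence. Its scope is "For common (2% within either treatment group) TEAEs, serious TEAEs and TEAEs leading to withdrawal of study medication", and for these "risk ratios along with 95% confidence intervals will be presented to compare treatment groups with respect to risk". No interval method is named, there is no instruction for a row with no events in one arm, and no risk difference is planned.

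The common-event table is by preferred term. The serious-event tables include "Treatment Emergent Serious AEs (TESAEs) by SOC and PT", and the withdrawal table has the same layout; neither has a minimum event count. The SAP does not say whether the serious and withdrawal ratios are given for each term or only overall.

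The rest of SAP 6.4.8 consists of by-arm counts, summaries, shifts and listings, and Protocol 10.4.4 names no between-arm contrast. Injection-site events as a group, and the list of 26 clinically relevant terms in SAP Appendix 6, are tabulated only. Protocol 1.3 states: "Injection site reaction is the only event known to be attributed to inclisiran treatment". Protocol 1.2.2.2 adds: "Injection site reactions have been reported in around 5% of subjects receiving either one or two doses of inclisiran". For the comparator, the Protocol synopsis says: "Placebo will be administered as SC injections of saline solution".

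**The concern.** A ratio needs events in the denominator arm. The rows of most interest in a safety review are those where every event is on the drug, and in these the planned measure yields no finite estimate. The programmer is left to choose between printing nothing, adding a half to each cell, or computing a score or exact bound. These choices can read differently on identical data, and by then the counts are known.

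The reaction already attributed to the drug fares no better. As a pooled group it has no contrast. A single injection-site term gets a ratio only if it reaches 2% in an arm, is serious or leads to withdrawal, and that ratio fails if saline produces no such event. What is at stake is how clearly the safety results can be read. The primary efficacy result is not affected.

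**Working it through.** **Inputs**
- Arm size: SAP 6.2 says "Due to faster than expected enrollment, actual enrollment was 482 subjects" and plans equal arms ("200 subjects will be randomized to inclisiran sodium 300 mg and 200 subjects randomized to placebo"). Assuming an equal split with everyone dosed, 482/2 = 241 per arm.
- Common-event threshold: 0.02 × 241 = 4.82, so 5 subjects in one arm (5/241 = 2.1%).
- Injection-site reactions on inclisiran: about 5% as a class, 0.05 × 241 ≈ 12 subjects.
- Not in the documents, so treated as ranges: per-term serious-event rates (0.05% to 2% per arm) and the placebo injection-site rate (0.25% to 2%).

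The documents state no precision or event rate for these ratios, so there is no plan figure to reproduce.

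**1. Behaviour of the ratio with a zero arm (241 per arm, inclisiran v placebo)**

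| Events | Risk ratio | Log-scale interval | Koopman score limit | Risk difference (Newcombe 95% CI) |
|---|---|---|---|---|
| 12 v 0 | not finite | none | above 3.16 | 5.0% (2.4% to 8.5%) |
| 5 v 0 | not finite | none | above 1.31 | 2.1% (0.1% to 4.8%) |
| 1 v 0 | not finite | none | above 0.26 | 0.4% (−1.2% to 2.3%) |
| 0 v 5 | 0 | none | below 0.76 | −2.1% (−4.8% to −0.1%) |

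Newcombe example, 12 v 0: the Wilson limits are 2.87% to 8.50% for 12/241 and 0% to 1.57% for 0/241. Lower limit = 4.98 − √((4.98 − 2.87)² + 1.57²) = 2.4%. Upper limit = 4.98 + √((8.50 − 4.98)² + 0²) = 8.5%.

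The unspecified method matters. Adding 0.5 to each cell turns 5 v 0 into a ratio of 11.0 (0.61 to 198), which includes 1; the score bound for the same data excludes 1. For 12 v 0 the half-cell ratio is 25.0 (1.49 to 420).

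**2. How often a row has a zero arm under equal risk**

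Given k subjects in the row, P(one arm zero) ≈ 2 × (1/2)^k = 2^(1−k): 100% for k = 1, 50% for k = 2, 25% for k = 3, 12.5% for k = 4. This needs no assumed event rate.

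By per-arm rate p, let q = (1 − p)^241. Among rows that appear, the share with a zero arm is 2q(1 − q)/(1 − q²) = 2q/(1 + q).

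| p | q | Share with a zero arm |
|---|---|---|
| 0.05% | 0.886 | 94% |
| 0.1% | 0.786 | 88% |
| 0.2% | 0.617 | 76% |
| 0.4% | 0.381 | 55% |
| 1% | 0.089 | 16% |
| 2% | 0.008 | 1.5% |

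The share is 50% when q = 1/3, so p = 1 − (1/3)^(1/241) = 0.45%, about one subject per arm. Under equal risk, half of the zero-arm rows have the zero on placebo.

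**3. Injection-site events**

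P(0 of 241 on placebo) = (1 − p)^241: 55% at 0.25%, 30% at 0.5%, 9% at 1%, 0.8% at 2%. It reaches 50% at p = 1 − 0.5^(1/241) = 0.29%.

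**The case against.** Several points against the concern are sound.

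- A reader might infer that the risk ratio has neither a value nor an interval whenever an arm is empty. That is too broad. With zero on inclisiran the ratio is 0, and score or exact limits exist on either side. Only the log-scale interval fails, and the SAP does not commit to it.
- A reader might infer that most serious-event rows are affected. The documents give no per-term rates, and it is true only below about 0.45% per arm. An overall row would rarely be affected, and the SAP does not say at which level the serious and withdrawal ratios are given. Under equal risk a common-event row, with at least 5 subjects in one arm, would seldom have an empty arm.
- The 5% injection-site figure is a class rate, so 12 v 0 illustrates the pooled group and should not be read as a forecast for one term. No ratio is planned for the pooled group that could fail. Zero events on saline are more likely than not only below about 0.29%.
- A reader might infer that rows with a usable ratio form a selected set favouring background events. The SAP drops no rows: counts and percentages appear for every row, and serious events and deaths are also listed. A 12 v 0 row would still show 5.0% against 0.0%.
- No safety hypothesis or decision rule depends on these ratios, and no measure makes a 1 v 0 row informative.

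These points narrow the concern without removing it. A visible difference without an interval is still not the comparison the SAP promises. The preference for a risk difference is also more than taste, because it stays finite in the rows where the ratio does not.

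**Conclusion.** The concern holds in a limited form. Within SAP 6.4.8 the risk ratio is the sole between-arm contrast, with no interval method and no zero-cell rule. Rows in which all events are on inclisiran get no finite estimate, and the pooled injection-site group gets no contrast.

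Under equal risk, serious or withdrawal rows of one to three subjects have a zero arm with probability of about 100%, 50% and 25%, if ratios are given by term. Whether such rows are the majority depends on rates the documents do not supply. Whether an injection-site term that qualifies as common has zero events on saline is likewise open. The figures by event rate and the intervals rest on an equal split of 482 with all subjects dosed. The point merits a change because the remedy is cheap and gives a clearer safety result; it does not bear on efficacy conclusions.

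**What to change.** Add a risk difference with a Miettinen-Nurminen or Newcombe 95% interval, naming the one chosen, to the common, serious and withdrawal adverse-event tables and to the pooled injection-site table. Show the risk ratio only where both arms have at least one event, and name its interval method. State whether the serious and withdrawal contrasts are given by preferred term or overall.

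The cost is one more column, computed from counts already tabulated. Intervals for single-event rows remain uninformative, as the 1 v 0 row above shows. The SAP addendum records that the database was locked and the study unblinded before its own changes, so this addition should be labelled as made after unblinding.
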